9.4 Sensitivity and Supportive Analyses of the Primary Outcome

Supportive Analyses

- The primary analysis will be repeated for the per-protocol population.
- As an *exploratory* analysis, the primary analysis may also be repeated for the modified intent to treat (MITT) population (defined below).
 - The MITT population in this study is defined as any randomized participants that received at least some of the study treatment (“randomized and treated”), defined as at least one SDM, MI, or CBT visit.
- Percentage change in daily MED from the baseline period also will be evaluated in a supportive analysis of the primary outcome. In this analysis, rather than change from baseline, each timepoints value will be calculated as the percent change, calculated as the change divided by the baseline score. The statistical model is the same.
- Compare the percentage of participants across intervention group that have met the clinically significant decrease in opioid use from baseline, defined as a decrease of 10 MED daily dose.
 - This analysis will be performed with a logistic mixed model for repeated measures (Proc GLIMMIX), similar to the method described in section 9.6.2 below.

Sensitivity Analyses - Assessment if Baseline Characteristics are Associated with Missing Outcome Data

This assessment will only be conducted if the percentage of participants with missing MED data at the 12-month timepoint is more than 20% in the ITT population.

A logistic regression model will be used to compare the demographic characteristics of participants who provided 12 months of EHR (prescription) data as compared with participants who were lost to follow-up within the EHR or withdrew consent for study participation to identify possible differential attrition. These characteristics will include but are not limited to: age, race, sex, baseline pain, baseline opioid use, co-

morbid health conditions, and others. In the event this logistic regression model indicates that a specific baseline characteristic is associated with a higher rate of attrition (or missing data), it can lead to biased results for both the primary and secondary outcomes.

If results of the logistic regression model indicate a specific baseline characteristic is associated with missing data, a sensitivity analysis on both the primary and secondary outcome measures will be implemented that run a similar model to those proposed in Sections 9.3 and 9.5 respectively, but the model will also include the baseline characteristic (i.e.: covariate) found to be associated with missing data.

Sensitivity Analyses - Multiple Imputation

This sensitivity analysis will only be conducted if the primary analysis identifies a statistically significant treatment group difference at 12 months in the ITT population and if the percentage of participants with missing MED at the 12-month timepoint is more than 20% in the ITT population. The MMRM analysis approach assumes missing data due to early study discontinuations are missing at random (MAR). As a sensitivity analysis to guard against bias if the MAR assumption is incorrect, a sensitivity analysis will be conducted on the primary outcome to assess the robustness of the primary analysis results using methods that assume that data are missing not at random (MNAR). Specifically, we will use multiple imputation of missing data to generate multiple imputed complete datasets, analysis of covariance on each dataset, and Rubin's rule to compare treatment groups across the imputed datasets (Ratitch, 2014). We will explore one sensitivity analysis called a tipping point analysis: impute missing outcomes in the intervention found to have a weaker change from baseline at varying percentages of the observed data (i.e., decreasing the observed MED) until a statistically significant treatment group difference is no longer identified (O'Kelly and Ratitch, 2014). This analysis tells us how much difference in the data could be present in order to still identify a statistically significant difference.

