## 5 STATISTICAL CONSIDERATIONS

### 5.1 Summary of Statistical Analysis

*Cross-reference: UNC IRBIS Application section A.8.1.*

Statistical analyses for this study have been designed to compare (1) the effectiveness of the 2 interventions (MI+CBT-CP and SDM) in reducing opioid dosage among patients with CNCP, and (2) the effects of the 2 interventions on pain interference and physical function. The analyses will use data collected at baseline, 6, 12, and 18 months to evaluate these effects, and will formally test the primary hypothesis that the reduction in opioid dose (absolute change in MED) differs between the 2 intervention arms at 12 months and will describe differences in absolute change in opioid dose at 6 and 18 months and percent change in dose at each timepoint. The analysis also will formally test intervention arm differences for 2 key secondary outcomes: change in pain interference and physical function at 12 months. Change in outcomes at 6 months will be described. Primary and secondary analyses will use model-based approaches that take advantage of the longitudinal structure of the outcome data to address missing data caused by patient loss to follow-up or nonresponse.

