5.2 Per-Protocol Population

As in most pragmatic clinical trials, some participants may not adhere to the intervention they were randomized to receive, reducing fidelity to the intervention as designed and potentially changing the effectiveness of the intervention. The most likely form of nonadherence will be absence from group therapy sessions in the MI+CBT-CP arm or with patients in the SDM arm ceasing interaction with the assigned provider. The potential impact of this nonadherence is underestimating the magnitude of the true treatment effect. To assess this, in addition to the ITT analyses, we will also conduct secondary analyses using a per protocol population consisting of participants that met all inclusion/exclusion criteria, and received a substantial portion of the randomized intervention, defined as at least 4 completed SDM visits and at least 4 completed MI or CBT sessions (out of a total of 1 MI and 8 CBT). Note that the inclusion criterion for baseline MED is based on the most recent prescription, while the baseline value for MED in the analysis is the average MED for the past 90 days. Having a baseline value < 20 is not a protocol violation when the sites indicated that inclusion criterion was met based on the most recent prescription when the patient was assessed. A sensitivity analysis on the per-protocol population will also be conducted by defining this population as those who met all inclusion/exclusion criteria and completed at least 3 SDM visits and at least 3 MI or CBT sessions. This sensitivity analyses are included as many SDM participants may only complete 3 visits with their provider throughout the 12-month intervention phase in the event their opioid prescriptions can be renewed over a 3-month period without an actual clinic visit.

The per-protocol analysis provides a better estimate of the true efficacy of an intervention (i.e., among those who completed the treatment as planned) (Ranganathan, Pramesh, & Aggarwal, 2016). No other analysis populations are defined for this protocol.

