9.2 Variable Definitions

The table below provides a description of the study endpoints and subgroup categories, including data type and derivation. More information regarding these variables is provided in the analysis dataset specification file.

Variable	Type	Definition
Primary Outcome		
Change in opioid dose (based on average daily MED) from baseline to 12 months post-randomization	Continuous	
The primary outcome will be derived from EHR data from the Mid-South CDRN data warehouse. Total morphine equivalents for each prescription will be calculated by multiplying the quantity of each prescription by the strength of the prescription (milligrams of opioid per unit dispensed). The quantity-strength product is then multiplied by conversion factors to estimate the milligrams of morphine equivalent to the opioids dispensed in the prescription. The total average dose in morphine equivalents per day supplied is calculated by summing the morphine equivalents for each prescription filled during a given period and dividing by the number of days supplied. The below algorithms further describe derivation of the primary outcome measure:
 $\text{One Prescription's MED Daily (MEDD)} = \frac{(\text{Strength per unit}) \times (\text{Quantity dispensed}) \times (\text{MME Conversion factor})}{(\text{Days Supply})}$ $\text{Avg. MEDD per Timeframe} = \frac{(\text{Multiply each RX's MEDD by Days Supply}) \text{ then } (\text{Sum all RX's Total MEDD for those prescriptions within timeframe})}{\text{Total number of days in timeframe}}$ 
Opioid dose will be calculated as the prescribed milligrams of daily MED averaged over the 90 days prior to randomization and averaged over 90-days for the time periods of 3, 6-, 9-, 12-, 15- and 18-months post randomization.
 
We expect no missing prescriptions, yet some participants might not have complete data because (a) they discontinued and removed consent to use data after that date, (b) they were lost to follow-up and may have moved out of the clinic's care, (c) the last CDM transfer did not contain their data up to 18 months past baseline or (d) they discontinued taking opioids. Cases of (d) will be identified by the response to the T2 and T3 survey item G20 "Are you currently taking an opioid medicine now?". If the response indicates "no" and opioid prescriptions last dose date ends before month 18, then an MED of zero will be assumed for all days after the last dose date to Month 18 (or date participant removed informed consent, if applicable). Otherwise, if there is not a "no" response

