
Variable	Type	Definition
		
to this item at the applicable T2 or T3 survey, or the survey was not completed, then the data after the last dose date ends will be considered missing in the calculation of the average MED across the 3-month time intervals.
 
NOTE: Section 5.3.1 in the protocol states the time periods of 4-, 6-, 8-, 10-, 12-, 14-, 16-, and 18- would be used; however, that was an inadvertent typo and it is correctly stated in protocol section 5.2.1.
 
For each of the post-randomization periods, change in daily opioid dose will be computed as the difference between the dose calculated during that period and the dose from the baseline period.
 
Further documentation regarding the medications included in the derivation of average daily opioid dose (MED) can be found in the supplemental file titled “INSPIRE_SAP_Suppl_Opioid_Meds”

Average percentage change in MED (based on average daily MED) from baseline period	Continuous	Percent change is calculated as the change from baseline divided by the baseline value. For example, if average baseline is 30 and average post baseline is 20, percent change is $(20-30)/30 =$ decrease of 33%. Alternatively, if average baseline is 30 and average post baseline is 40, average percent change is $(40-30)/30 =$ increase of 33%.
Average relative amount of MED from baseline (based on average daily MED)	Continuous	
If warranted based on evaluation of the data prior to database lock, we may evaluate average relative change rather than actual change – defined as the value in the post baseline timepoint divided by the baseline value.
 
For example, if average baseline is 30 and average post baseline is 20, average relative change is $20/30 = 2/3$rds of the average baseline MED.
 
If determined not warranted, this variable will not be calculated.

Indicator for change from BL of at least 10 MED	dichotomous	Calculated at 3, 6, 9, 12, 15, 18
Secondary Outcomes		

Variable	Type	Definition

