Substance Use Disorders Flag(s)	Binary	
Includes an indicator for any substance use disorder recorded as a diagnosis in the EHR, as well as binary indicators for the presence in the EHR of each of the following: alcohol use disorder and substance use disorder.
 
The ICD-10 codes used to identify Substance Use Disorders was pulled from the Healthcare Cost and Utilization Project Agency for Healthcare Research and Quality (H-CUP-AHRQ) website (https://hcup-us.ahrq.gov/toolssoftware/ccs10/ccs10.jsp#download)

Age	Continuous and categories	
As reported on the T1 (baseline) survey and captured in REDCap.
 
Age category will also be calculated as:
 
 < 50 50-64 >= 65
Intervention Delivery Mode	Categorical and Binary	
Due to the COVID-19 pandemic, the study began offering telehealth intervention visits beginning in early-May 2020. The intervention visit Case Report Forms (CRFs) were modified to document if a specific intervention visit was administered via telehealth or in-person visit. Since the CRFs were not modified until early-August 2020, all visits up-to-that point will be defined as in-person visits. Descriptive statistics of intervention delivery mode by intervention will be displayed (in-person only, telehealth only, and mixed mode); however, for adjusted analyses, mixed mode will be combined with telehealth to create a binary classification variable.

Variable	Type	Definition
Baseline Opioid MED categories	Ordinal	See the first row in this table regarding the derivation of average daily opioid prescription (in MED). Prescriptions provided 3-months, or 90-days prior to randomization will be considered a participant's baseline opioid MED, classified as None (0 MED), Very low (1-<20 MED) Low (20 - <50 MED), Moderate (50 - <90 MED), and High (90+ MED).
BMI	Continuous and categories	
Derived based on the participant's weight and height obtained from the EHR data (pulled within 90-days of the randomization date).
 
BMI category will also be calculated as:
 
 underweight: <18.5 normal 18.5 - < 25 Overweight 25 - < 30 Obese 30 - <40 Extremely obese >=40 
A dichotomous flag will also be calculated for BMI obese vs not obese.

Sex	Binary	As collected from the T1 (baseline survey); based on birth certificate.

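### Percent change in MED is undefined at a zero baseline and unstable at very low ones, and the SAP has no rule for either

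*SAP*

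**What the plan says.** SAP 9.4 lists percent change in daily MED as a supportive analysis of the primary outcome: "each timepoints value will be calculated as the percent change, calculated as the change divided by the baseline score". It adds "The statistical model is the same", meaning the repeated-measures linear model of SAP 9.3. SAP 9.2 defines the same participant-level ratio: "Percent change is calculated as the change from baseline divided by the baseline value". Neither section sets a minimum denominator or a rule for a denominator of zero.

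The denominator is not the dose that made the participant eligible. SAP 5.2 notes that eligibility uses the most recent prescription, "while the baseline value for MED in the analysis is the average MED for the past 90 days". The displayed formula in SAP 9.2 divides the summed morphine equivalents by "Total number of days in timeframe", so days without supply lower the average. The prose in the same table row, and in Protocol 4.1.1, divides by the number of days supplied instead.

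Low values are foreseen. Baseline dose is "classified as None (0 MED), Very low (1-<20 MED") and three higher classes. SAP 5.2 states "Having a baseline value < 20 is not a protocol violation" where the site confirmed eligibility on the most recent prescription. SAP 4.4.3 has such cases queried with the site, but does not exclude them.

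Protocol 5.1 and SAP 9.1 undertake to describe "percent change in dose at each timepoint". Protocol 5.2.1 calls percent change a secondary analysis.

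**The concern.** A participant-level ratio needs a denominator safely away from zero, and the SAP's own baseline classes show that this one may not be. At a baseline of exactly zero the value does not exist. Near zero, a short supply window before randomization looks like a very large dose increase afterwards, whereas a decrease can never go below -100%. The error is therefore one-sided and works against showing dose reduction. The planned model adjusts for baseline linearly and assumes one residual variance per arm, so it does not absorb values that behave like one over the baseline.

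At stake is the percent-change result that readers will see beside the absolute primary result. Its arm difference and standard error could reflect how a small group's prescriptions fell in the 90 days before randomization more than what the interventions did.

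**Working it through.** **1. The plan's own example.** SAP 9.2: (20 - 30)/30 = -33% and (40 - 30)/30 = +33%. Both reproduce.

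**2. Zero baseline.** Percent change is (Y - 0)/0, undefined at every month, so the participant contributes no record to this analysis. The absolute change, Y - 0, is defined, so the same participant stays in the primary model.

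**3. Low coverage, by the displayed SAP formula.** One 20 MED/day prescription covering d of 90 days gives baseline 20d/90. Steady use at 20 MED afterwards scores 100(90/d - 1)%.

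| d | Baseline MED | Percent change |
|---|---|---|
| 5 | 1.1 | +1,700 |
| 7 | 1.6 | +1,186 |
| 15 | 3.3 | +500 |
| 30 | 6.7 | +200 |
| 60 | 13.3 | +50 |
| 90 | 20.0 | 0 |

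**4. Effect on the SD.** Assumptions, none from the documents: follow-up dose is 0.9 x usual dose with log-SD 0.4, and 5% of participants have low coverage.

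Let R be follow-up divided by usual dose. Its mean is 0.9 x e^0.08 = 0.975 and its SD is 0.975 x sqrt(e^0.16 - 1) = 0.406.

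- *Everyone fully covered:* mean -2.5, SD 40.6 points.
- *5% with 30 of 90 days:* in that group percent change is 100(3R - 1), with mean 192.5 and SD 121.8. The overall mean is 0.95 x (-2.5) + 0.05 x 192.5 = 7.25. Variance from the 95%: 0.95 x (40.6² + 9.75²) = 1,656. Variance from the 5%: 0.05 x (121.8² + 185.25²) = 2,458. SD = sqrt(4,114) = 64; the 5% supply 2,458/4,114 = 60%.
- *5% with 5 to 30 whole days, equally likely:* 90/d has mean 6.617 and mean square 58.74. The group mean is 100(6.617 x 0.975 - 1) = 545, and its variance is about 239,000. The overall mean is 24.9. The 5% contribute 0.05 x (239,000 + 520.3²) = about 25,485 and the rest 0.95 x (1,648 + 751) = about 2,279. SD = sqrt(27,764) = 167; share 92%.
- *5% with baseline uniform on 1 to 5 MED, unrelated to usual dose:* by simulation, with usual dose lognormal (mean 55, SD 80, from Protocol 5.4) kept if at least 20. SD about 1,300, share about 99%.
- *Mild case, 5% with coverage spread over 30 to 90 days:* by simulation, SD about 46, share about 26%.

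**5. Planned summary against an arm-level one.** Simulation: 4,000 runs; 526 x 0.88 = about 462 evaluable (SAP 6); one 12-month analysis of covariance standing in for the repeated-measures model; true arm effect -15% of usual dose; very low baselines uniform on 1 to 20 MED and unrelated to usual dose, which is on the severe side. Entries are mean (SD) of the estimated arm difference, in percentage points.

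| Zero / very low | Lost | Individual percent change | Arm-level percent change |
|---|---|---|---|
| 0% / 0% | 0 | -14.8 (3.2) | -14.7 (3.8) |
| 0% / 2% | 0 | -17.2 (16.2) | -15.0 (4.0) |
| 1% / 5% | about 5 | -20.4 (24.3) | -15.5 (4.5) |
| 2% / 10% | about 9 | -26.1 (34.2) | -16.4 (5.2) |
| 5% / 20% | about 23 | -36.5 (48.1) | -18.6 (6.5) |

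The arm-level figure drifts a little because low baselines reduce the mean it is divided by, but its precision holds.

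**The case against.** The strongest reply has four parts.

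- **No document reports a participant at 0 or at a few MED.** SAP 3.1.3 and 9.6.5 list baseline classes from very low upward only, and SAP 4.4.3 queries averages below 20, which should remove spurious ones. This stands as a limit on size. The classes below 20 are additions to those in Protocol 5.3.3, which suggests such cases exist but does not prove it.
- **There is a fallback.** SAP 7.1 provides for transformation or non-parametric tests when normality of a continuous outcome is substantially violated, and SAP 9.3 asks for residual plots. This may soften the outlier problem. It names no method and cannot supply a value where the denominator is zero. The normality finding in SAP 9.3 concerned absolute change and says nothing about percent change.
- **The divisor is unsettled.** If the average is taken over days supplied, as the prose has it, gaps in supply do not pull the baseline down and very low values become rarer. This stands. A zero baseline remains undefined either way.
- **The stakes are limited.** The analysis is supportive and descriptive. The primary test and the 10-MED responder analysis need no division by baseline. This stands.

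A reader might go further and infer that a handful of extreme values will dominate, with an SD near 1,300. That needs baselines of 1 to 5 MED unrelated to usual dose. Protocol 5.2.3 describes prescriptions as generally running 30 days, and one such supply at the 20 MED minimum already gives 6.7. A reader might also say that the analysis abandons intention to treat. SAP 5.1 includes randomized participants wherever data are available. The narrower point is that a zero-baseline participant has dose data, but the chosen formula cannot use them.

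**Conclusion.** The gap is real and its mechanism is fully documented: an individual ratio, a denominator the SAP itself classes as possibly 0 or 1 to under 20 MED, and no handling rule. Loss of any zero-baseline participant follows by arithmetic. The extra weight of low-coverage participants follows too, but its size is not known from the documents. With an assumed 5% at low coverage, the SD goes from about 41 to about 64, 167 or 1,300 points, and that 5% supplies about 60%, 92% or 99% of the variance; with milder gaps the SD is about 46. All these figures use the total-days divisor or impose the low baseline directly, and shrink if days supplied is the divisor.

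The documents do not support the inference that the primary result is at risk. The absolute-change test is unaffected. This is a defect worth correcting in a planned, reported, non-primary analysis.

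**What to change.** In SAP 9.2 and 9.4, define percent change at arm level:

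- For each arm and timepoint: 100 x (LS-mean MED change from the primary model) / (mean baseline MED pooled over both arms).
- For the arm difference: 100 x (difference in LS-mean change) / (the same pooled mean).
- Bootstrap 95% confidence intervals for each arm and for the difference, resampling participants and keeping everyone in the primary model.
- Report by arm the number with baseline 0 and with baseline 1 to under 20 MED.

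Do not instead restrict the analysis to baselines of at least 20 MED. That would drop every participant below 20, including those SAP 5.2 expressly accepts, and so lose more randomized participants than the zeros alone.

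The cost is a wording change and one bootstrap step. The summary becomes a ratio of means, not a mean of individual ratios, so it answers a slightly different question and is close to a rescaling of the primary estimate. It is slightly less precise if no low baselines occur (SD 3.8 against 3.2 points in the simulation above).

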6. SAMPLE SIZE DETERMINATION

Sample size estimates were generated to provide robust power to detect minimal clinically important differences (MCID) in reduction of opioid use between the 2 study arms.

A total sample size of 506 participants (253 per study arm) will provide 80% power to detect an effect size of a difference of 10 MED between the SDM and MI+CBT intervention arm using an analysis of covariance model with $\alpha=0.05$ and assuming a baseline model-adjusted standard deviation for change from baseline of 40 MED. The sample size was inflated by 20% (608 total participants; 304 per study arm) to account for potential variance inflation associated with CBT group delivery (based on a group

size of 8 and an interclass correlation coefficient of 0.01) and a potential loss of follow-up opioid prescription data on as many as 12% of participants.

For the PROMIS secondary outcome measures, the minimally important difference (MID) for the physical function scale is 2 units, whereas the MID for the pain interference scale is 3.5 units. For both instruments, we assume the standard deviation for change from baseline is 10 (see section 9.2 for a more thorough description of these secondary measures). With the planned total of 608 randomized participants and assuming 20% of those have missing PROMIS scale responses, the power for the PROMIS Pain Interference score is 96%, while the power for the PROMIS Physical Functioning scale is 57% (Table 6.1).

Note that the enrollment was slower than planned, and due to timeline constraints was stopped prior to reaching 608 randomized participants. Final study enrollment was 526 randomized participants. As of June 2023 (DSMB report), study discontinuation was at 20%;, but survey completion rate was tracking around 60% (40% missing, higher than the planned levels). Approximate post-hoc power based on the final sample size is provided in Table 6.1.

Table 6.1. Power for Primary and Key Secondary Outcomes

Total sample size	Primary aim: Power for opioid MED ¹	Secondary aim: power for PROMIS Pain Interference ²	Secondary aim: Power for PROMIS Physical Functioning ²
Planned 608	80%	96%	57%
Approximate post hoc power based on randomized (n=526)	75% based on protocol- assumed level of missing opioid prescription data	85% Based on number of completed surveys	40% Based on number of completed surveys

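### The covariate-adjusted missing-data sensitivity analysis for PROMIS is triggered by missing opioid-dose data, and takes its covariates from EHR loss, so it may not run or may miss the predictors of survey non-response.

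*SAP*

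**What the plan says.** SAP 9.4 sets out a step that looks for baseline characteristics linked to missing outcome data.

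- **Trigger.** "This assessment will only be conducted if the percentage of participants with missing MED data at the 12-month timepoint is more than 20" per cent in the ITT population.
- **What is modelled.** A logistic regression compares "participants who provided 12 months of EHR (prescription) data as compared with participants who were lost to follow-up within the EHR or withdrew consent".
- **Where the result goes.** If a characteristic is flagged, "a sensitivity analysis on both the primary and secondary outcome measures will be implemented", using the models of 9.3 and 9.5, and "the model will also include the baseline characteristic (i.e.: covariate) found to be associated with missing data".

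SAP 9.5.1 analyses PROMIS physical function and pain interference with a mixed model analogous to 9.3, under MAR, using the 6- and 12-month scores. Neither 9.4 nor 9.5.1 uses survey completion as a trigger or as a modelled outcome. The other sensitivity analysis in 9.4, the tipping-point imputation, covers the primary outcome only and also has a MED trigger.

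On rates, SAP 6 allows for "a potential loss of follow-up opioid prescription data on as many as 12% of participants" and reports that, as of June 2023, "study discontinuation was at 20" per cent and "survey completion rate was tracking around 60% (40% missing, higher than the planned levels"). Protocol 5.3.3 also plans the two sources separately: up to 25% survey non-response and up to 12% missing EHR dose data at 12 months.

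**The concern.** PROMIS scores and MED values come from different sources and can be missing separately. Under Protocol 3.12, a participant who withdraws after some intervention gives no further survey data but may agree to continued EHR extraction. SAP 8.1 describes participants who could not be contacted yet stayed in the study for survey invitations and EHR extraction. Both routes can leave PROMIS missing with MED present.

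A rule keyed to MED can therefore fail PROMIS in two ways. It may not open, although surveys are missing well above the same 20% level. If it opens, it looks for predictors of EHR loss and may pass over a characteristic that drives survey non-response.

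At stake is the check on the two secondary outcomes that are formally tested with the Hochberg adjustment (SAP 7.6). Protocol 5.3.3 itself names physical function and pain interference among the outcomes that attrition may be linked to, and leaves the MAR sensitivity analyses to the SAP. This step is the only one in the SAP that reaches those outcomes.

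**Working it through.** **Inputs.** From SAP 6: N = 526; survey missingness 40%; discontinuation 20%; planned MED loss 12%; PROMIS SD of change 10; MIDs of 2 (physical function) and 3.5 (pain interference); CBT group size 8 and ICC 0.01. From SAP 9.4: trigger above 20%.

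**1. The plan's own figure.** SAP Table 6.1 gives post hoc PROMIS power of 85% and 40%, based on completed surveys. The design effect is 1 + (8 − 1) × 0.01 = 1.07, so the effective N is 526 × 0.60 / 1.07 = 295, or 147.5 per arm. Power = Φ(δ / (10 × √(2/147.5)) − 1.96), and the standard error is 1.16.

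- δ = 3.5: Φ(3.01 − 1.96) = 85.2%
- δ = 2: Φ(1.72 − 1.96) = 40.4%

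The table reproduces with 40% missing. It also fits 45% missing with no design effect (84.5% and 39.8%), so it does not fix the month-12 rate exactly. Either rate is at least twice the 20% threshold.

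**2. Counts against the trigger.** 20% of 526 is 105.2, so at least 106 MED values must be missing.

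| Quantity | Arithmetic | Participants |
|---|---|---|
| Planned MED loss | 0.12 × 526 | 63 |
| Reported discontinuation | 0.20 × 526 | 105 |
| Missing surveys, if 40% applies at month 12 | 0.40 × 526 | 210 |

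**3. Chance that the trigger fires.** This is P(X ≥ 106) for X ~ Binomial(526, p). The true p is not reported, so each row is an assumption.

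| Assumed MED missingness | Chance of firing |
|---|---|
| 12% or 15% | below 0.1% |
| 18% | 11% |
| 20% | 48% |
| 22% | 86% |
| 25% or more | above 99% |

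**4. Which predictors would be found.** In 1,000 simulated trials of 526, a 50:50 baseline factor had survey non-response of 50% against 30% and was unrelated to EHR loss. A 5% chi-square test on EHR loss flagged it in 3.8% of runs (EHR loss 12%) and 5.3% (EHR loss 25%), which is chance level. The same test on survey non-response flagged it in 99.9% and 99.4%. No relation to EHR loss is the limiting case; overlap between the two would raise the first pair.

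**5. Size of a bias that could go unexamined (illustration).** Assume a 50:50 factor worth g = 3 to 5 T-score units beyond the baseline score. Among completers, the bias in the arm contrast is g × (difference between arms in the factor's share of responders). With response of 70% and 50% by factor level, the share is 0.70 / (0.70 + 0.50) = 0.583; reversed, it is 0.417; with equal response, it is 0.50.

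- Same pattern in both arms: 0.583 − 0.583 = 0, so no bias.
- One arm only: 0.583 − 0.50 = 0.083, giving 0.25 (g = 3) to 0.42 (g = 5).
- Opposite directions: 0.583 − 0.417 = 0.167, giving 0.50 to 0.83.

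Against the 2-unit physical-function MID, the one-arm case is 12.5% to 21% and the opposite-direction case 25% to 42%. These are complete-case figures. The 9.5.1 model also uses month-6 scores, which should reduce the bias somewhat for participants who returned that survey.

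**The case against.** The strongest reply is that the two kinds of missingness are linked. SAP 4.6 stops both surveys and EHR extraction after full withdrawal. SAP 9.2 treats dose data after the last prescription as missing unless the applicable survey contains a report of no longer taking opioids, so an unreturned survey can itself make MED missing. With discontinuation already at 20%, the trigger may well fire, and some predictors may be shared. This stands, and it rules out saying that the analysis will not run or that its indicator is unrelated to PROMIS. It does not make EHR loss a substitute for survey non-response.

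The section is also headed as analyses of the primary outcome, the rule can be executed as written, and the main PROMIS models do not depend on it. That is correct and limits the point to a sensitivity analysis.

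Three stronger readings are tempting, and the documents do not support them.

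- A reader might take 210 missing month-12 surveys as a reported count. SAP 6 gives one overall completion rate and does not tie it to the month-12 survey.
- A reader might infer a bias of 0.5 to 0.8 units. That needs a factor acting in opposite directions in the two arms, and nothing in the documents suggests one.
- A reader might infer that leaving arm out of the logistic model causes bias. Arm and arm-by-time are in the mixed model (SAP 9.3), so attrition that differs by arm alone is ignorable under MAR. Only attrition that depends on arm and a characteristic together matters here.

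**Conclusion.** The point holds as a gap in a sensitivity analysis. SAP 9.4 decides whether PROMIS gets a covariate-adjusted missing-data analysis from the amount of missing MED, and chooses the covariates from a model of EHR loss or consent withdrawal. On the planned 12% MED loss it would almost certainly not run. The actual rate is unreported, and near 20% the outcome is about even. If it runs, it can still miss predictors of survey non-response.

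The main PROMIS estimates, tests and stated power do not change. The bias at issue is illustrative: about 0.25 to 0.4 units if an assumed factor worth 3 to 5 units acts in one arm only, zero if the pattern is the same in both arms, and 0.5 to 0.8 only in the extreme opposite-direction case. It is worth correcting because the overall survey loss is about twice the plan's own 20% threshold and no other sensitivity analysis covers these two outcomes.

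**What to change.** Split the step in SAP 9.4.

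- **MED.** Keep the EHR model and the MED trigger, for the primary outcome only.
- **PROMIS.** Fit a separate logistic model of 12-month survey completion on a pre-specified set of baseline characteristics. Include arm and arm-by-characteristic terms, to show attrition patterns that differ by arm. Run it unconditionally, or trigger it on survey missingness above 20%; at the reported overall rate that trigger would be met.
- **Use of the result.** Add the pre-specified or flagged covariates to the 9.5.1 mixed models as a sensitivity analysis only, and say so, so that data-driven selection cannot alter the formally tested PROMIS models. A covariate set fixed in advance is simpler; if flagging is used, state the flagging rule beforehand.

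The cost is SAP wording and one more regression on data already held. Sample size and stated power are unaffected.
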